2.1. Statistical Hypotheses

The null hypothesis corresponding to the primary estimand is:

- Null hypothesis H0: IXT-m200 is not different from placebo with respect to the group means for the percent of 20 weeks abstinent from stimulants.
- Alternative hypothesis H1: There is a difference between IXT-m200 and placebo with respect to the group means for the percent of 20 weeks abstinent from stimulants.

The null and alternative hypotheses for all secondary estimands will be defined similarly, with the null hypothesis being "no difference" between groups, and the alternative hypothesis being "there is a difference," (i.e. a two-tailed alternative).

2.2. Sample Size Determination

As this is an exploratory Phase 2A study, the sample size was not set to power the study to statistically detect any particular treatment effect. Instead, it was chosen to balance the need to gather sufficient information regarding treatment effect and variability to plan for Phase 3, while not exposing more subjects than necessary to any yet unknown safety concerns.

Still, an assessment of the potential power of the study for statistical testing is provided in Table 4. These estimates assume that cohort 2 (if conducted) receives a different dose of IXT-m200, and provide the power for comparing *each* dose group to placebo. The primary endpoint will be based on Cohort 2, but cohorts may be pooled to perform additional analyses.

Table 4. Minimum detectable difference between *each* IXT-m200 group versus the placebo group

	placebo group								
	Detectable	Examples of detectable differences with varying pooled SD							
Power	difference	20%	25%	30%					
Cohort 1/	Cohort 2 only								
$(n_1 = 40 \text{ vs})$	$s n_2 = 20$)								
0.80	$0.78 \times \text{pooled SD}$	15.6%	19.5%	23.4%					
		(3.1 more weeks)	(3.9 more weeks)	(4.7 more weeks)					
0.85	$0.84 \times \text{pooled SD}$	16.7%	20.9%	25.1%					
		(3.3 more weeks)	(4.2 more weeks)	(5.0 more weeks)					
0.90	$0.90 \times \text{pooled SD}$	18.1%	22.5%	27.1%					
		(3.6 more weeks)	(4.5 more weeks)	(5.4 more weeks)					
Cohorts 1	and 2 pooled								
$(n_1=40 \text{ vs})$	$s n_2 = 40$)								
0.80	$0.63 \times \text{pooled SD}$	12.6%	15.8%	18.9%					
		(2.5 more weeks)	(3.2 more weeks)	(3.8 more weeks)					
0.85	$0.68 \times \text{pooled SD}$	13.6%	17.0%	20.4%					
		(2.7 more weeks)	(3.4 more weeks)	(4.1 more weeks)					
0.90	$0.73 \times \text{pooled SD}$	14.6%	18.3%	21.9%					
		(2.9 more weeks)	(3.7 more weeks)	(4.4 more weeks)					

The detectable differences were calculated in SAS Proc Power using a two-sample t-test assuming equal variance a two-sided 5% alpha. SD = standard deviation.

The literature suggests that dropout rates in the study population may be up to 50% Error! Bookmark not defined, and therefore the analyses will account for missing data.

2.3. Multiplicity Adjustment

As this is an exploratory Phase 2 study, no adjustments for multiplicity will be made.

2.4. Interim Analyses

An interim analysis will be conducted after the last participant in Cohort 1 has available Week 25 data (or has previously discontinued). This interim analysis will include an unblinded review of efficacy, in addition to the typical safety report content.

As a Phase 2 study, there will not be formal statistical stopping rules for efficacy or futility. A Data Safety Monitoring Board (DSMB) will review the interim report (see the following Section 2.4.1 for further details) and provide a non-binding recommendation to the sponsor regarding the conduct of the study moving forward.

2.4.1. Data Safety Monitoring Board

The DSMB will review an interim analysis report after the last participant in Cohort 1 has available Week 25 data (or has previously discontinued) at which time the DSMB will review efficacy in addition to the typical safety report content. On the basis of the Week 25 interim analysis, the DSMB may recommend whether to proceed to Cohort 2, and if proceeding, which dose to use for the IXT-m200 group (e.g., escalate to 3.0 g, continue at 1.5 g, or reduce). If the DSMB recommends continuing dosing at 1.5 g in Cohort 2, a sample size recalculation will be executed using the pooled standard deviation of the primary endpoint in Cohort 1. The DSMB may also recommend that the study be stopped early if there is sufficient evidence that any of the following circumstances apply.

- Determination of unexpected, significant, or unacceptable risk to participants either related to the study intervention or unrelated events (such as a national health emergency);
- Demonstration of efficacy that would warrant early termination;
- Insufficient compliance to protocol requirements;
- Data that are not sufficiently complete and/or evaluable;
- Determination that the primary endpoint has been met;
- Determination of futility.

The Sponsor will make the ultimate decision as to whether to accept the DSMB's recommendation. The Sponsor may have access to group-level data but will not have access to unblinded participant-level data at the time of the interim analysis. The Sponsor will have ongoing access to blinded individual participant data from saliva tests and daily self-reported drug use surveys. Participants will continue the study in Cohort 1 through Week 33 while the interim analysis is ongoing.

3. Analysis Sets

For the purposes of analysis, the following analysis sets are defined:

Table 5 Analysis Populations

Participant Analysis Set	Description						
Intent-to-treat (ITT)	The intent-to-treat (ITT) population will be comprised of all randomized participants categorized by their randomized treatment assignment.						
Modified intent-to-treat (mITT)	The modified ITT (mITT) population will be comprised of all randomized participants who received at least one dose of study drug. Participants will be analyzed according to their randomized treatment assignment.						
Per protocol (PP)	The per-protocol (PP) population will be comprised of participants in the mITT population who had no major protocol deviations with the potential to impact efficacy assessments. Participants will be analyzed according to the treatment which they received (i.e., a participant randomized to placebo who received only active study drug in error will be analyzed with active participants, and a participant randomized to active who received only placebo will be analyzed with the placebo participants). The PP population will exclude participants who received some active drug and some placebo. InterveXion will conduct a blinded review of the protocol deviations prior to database lock to determine if any participant should be excluded from the PP population.						
Safety	The safety population will be comprised of all randomized participants receiving at least one dose of study drug. Subjects will be classified according to drug actually received.						
Pharmacokinetic (PK)	The pharmacokinetic population will include all subjects for whom a serum concentration of IXT-m200 is available post-dose.						
PK Concentration	This set will include subjects who received at least one dose of study drug and have at least one quantifiable serum concentration of IXT-m200 post-dose. Subjects with an insufficient number of PK samples to derive PK parameters or those not in the PK subset will still be used for listing and summary of PK concentrations, along with any graphical presentations of concentration-time data.						
PK Parameter	Any subjects in the PK subset for whom the PK profile can be adequately characterized. These will be decided by Pharmacokinetic Personnel.						

The ITT population will be used to analyze endpoints related to the efficacy objectives, and the safety analysis set will be used to analyze all endpoints and assessments related to safety. If less than 90% of the ITT population is in the PP population, then efficacy objectives will also be

analyzed using the PP population as sensitivity analyses. Immunogenicity will be assessed using the mITT population. PK concentrations will be derived using the PK concentration set and PK parameters will be derived using the PK parameter set.

4. Statistical Analyses

4.1. General Considerations

While statistical inference regarding the treatment effect of IXT-m200 on MUD is an important aspect of the analysis of this trial, it should be noted that this trial is also intended to gather information regarding the feasibility of various endpoints and measures of MUD treatment response. There has been relatively little described in the literature with respect to pharmacological treatments, and thus there is a lack of precedence with regard to the most efficient measures. Therefore, this analysis plan incorporates a range of endpoints/estimands and sensitivity analyses, from primary through exploratory, which vary the definition of response to treatment, and will allow an assessment of the utility of each to measure treatment effect.

4.1.1. Common Statistical Methods and Data Presentations

Descriptive and inferential statistics will summarize results. Unless otherwise indicated, the prespecified efficacy analyses will be conducted using the ITT population. The study will use an overall nominal two-sided Type I error rate of 5%; results will be reported with a two-sided 95% confidence interval (CI) and nominal p-value. For primary and selected secondary and exploratory efficacy outcomes, plots of the cumulative distribution functions (CDFs) will show differences by treatment arm.

Categorical variables will be summarized with the frequency count and percentage of participants with non-missing data. Continuous variables will be summarized using appropriate summary statistics (e.g., the number of non-missing observations, mean, standard deviation (SD), median, 25th and 75th percentiles, minimum, maximum; geometric mean and 95% confidence intervals (CIs) may also be presented, as appropriate).

All summaries will be by treatment group. Tabular presentations will display a separate column for each treatment regimen and graphical summaries will color-code each treatment regimen.

In addition to tabular and graphical summaries, by-participant listings will present all relevant electronic case report form (eCRF) data, sorted by treatment group and participant identifier.

4.1.2. Other Missing Data, and Data Errors

Any missing values for treatment responder endpoints will be imputed as "non-responder." Missing values for global impressions scales will be imputed as the neutral result of "No Change."

For endpoints related to saliva screens or self-report surveys, if a participant withdraws from the study, all remaining days following withdrawal will be imputed as not abstinent.

Missing values for quality of life, as measured by the Treatment Effectiveness Assessment, will not be imputed. Participants who withdraw or discontinue prior to Week 5, or do not have any reported saliva or self-report use data between Weeks 5 and 25 will not be included in the analysis.

In general, missing and partial dates will be displayed as captured in participant listing displays. For adverse events:

- Missing start day: first of the month will be used unless this is before the start date of study drug; if the partial date is the same month as the first dose of study drug, the treatment start day will be used and the event will be considered treatment-emergent.
- Missing stop day: the last day of the month will be used.
- Completely missing start or end dates will remain missing, with no imputation applied. Time to onset will be missing, and duration will be considered ongoing.

For concomitant medications/medical history:

- If the partial date is a start date, January and 1 will be used for a missing month and missing day, respectively.
- If the partial date is a stop date, December will be used for a missing month, and the end of the month will be used for a missing day (i.e., 28/29/30/31 dependent on the month and year of the partial date).

For pharmacokinetic purposes, missing concentration data will be considered as non-informative and will not be imputed. No concentration estimates will be provided for missing sample values.

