7.2 PARTICIPANT DISCONTINUATION/WITHDRAWAL FROM THE STUDY

Participants who withdraw consent for dosing and all future study visits (following early termination assessments) will be considered ‘withdrawn’. Participants are free to withdraw at any time upon request; they will be asked to complete early termination assessments as soon as possible.

Participants that will no longer be dosed with study drug but agree to continue participation in other study procedures and assessments will be considered ‘discontinued’. Participants are free to discontinue at any time upon request. Participants will be encouraged to complete study visits, assessments, and therapy sessions, even if they elect to discontinue study drug administration. In this case, all study activities will be completed per protocol with the exception of dose administrations.

An investigator may discontinue a participant from study drug administration for the following reasons:

- the participant meets an exclusion criterion (either newly developed or not previously recognized) that precludes further study participation, such as pregnancy,

- any clinical AE, laboratory abnormality, or other medical condition or situation occurs such that continued participation in the study would not be in the best interest of the participant,
- significant non-compliance by the participant,
- if, in the investigator's opinion, continuation with study drug administration would be detrimental to the participant's well-being,
- at the specific request of Sponsor or the investigator.

Participants who miss dosing days and return to the study at a later point are not automatically disqualified from resumption of dosing. Please discuss with Sponsor if two or more consecutive dosing visits are missed and the participant later wishes to resume treatment.

In all cases, the reason for withdrawal or discontinuation must be recorded in the eCRF and in the participant's medical records. If the reason is not known, an attempt must be made to follow up with the participant to establish whether the reason was an AE, and, if so, this AE must be reported. Once the participant has been contacted and expresses their decision to withdraw from further participation in the study, the research staff will cease to try to make further contact.

There will be no replacement of participants who withdraw or are discontinued following the first dose of study drug.

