1.1. Objectives, Endpoints, and Estimands

The following Table 2 lists the primary and secondary efficacy objectives of the study, along with the endpoints that will be measured, the clinical question to be addressed, as well as the estimand. An estimand is defined in the ICH E9(R1) guidance as "...the target of estimation to address the scientific question of interest posed by the trial objective."

Table 2 Primary and Secondary Efficacy Objectives, Endpoints and Estimands

Primary		
Objective: To evaluate the efficacy of IXT-m200 in preventing or	Endpoints: Percent of 20 weeks abstinent from stimulants following a 4-week grace period (between Week 5 and Week 25) as measured by saliva screens.	
reducing relapse to stimulant use.	Clinical Question: Does adding IXT-m200 to standardized cognitive behavioral therapy (CBT) program improve the percent of 20 weeks abstinent from stimulants following a 4-week grace period, relative to the CBT program alone, in treatment-seeking participants, regardless of IXT-m200 interruption or discontinuation, for any reason?	
	Estimand: The difference in group means between the IXT-m200 and placebo groups for the percent of 20 weeks abstinent from stimulants following a 4-week grace period as measured by saliva screens in treatment-seeking individuals with MUD. All observations will be used, regardless of whether a participant discontinued treatment early. All missing values will be imputed assuming the participant is not abstinent.	
	Secondary	
Objective: To evaluate the efficacy of IXT-m200 in improving	Endpoints: Change from screening in participant-rated quality of life as measured by the Treatment Effectiveness Assessment (TEA) at Week 13, 25, and Week 33.	
participant-rated quality of life.	Clinical Question: Does adding IXT-m200 to standardized CBT program improve the change from screening in participant-rated quality of life relative to the CBT program alone in treatment-seeking participants regardless of IXT-m200 interruption or discontinuation, for any reason?	
	Estimand: The difference in group medians for the change from screening in participant-rated quality of life at Week 13, 25, and 33 between the IXT-m200 and placebo groups. All observations will be used, regardless of whether a participant discontinued treatment early. Missing values will not be imputed.	

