4.7.1.2. Main analytical approaches

All secondary analyses will use the ITT population.

Quality of life analysis

A secondary objective is to evaluate the efficacy of IXT-m200 in improving patient-rated quality of life, as measured by change from screening in the Treatment Effectiveness Assessment score at Week 13, Week 25, and Week 33.

The Treatment Effectiveness Assessment includes four items with 10 ordinal response options ranging from "not well at all" to "extremely well" (Likert scale), where higher values indicate better quality of life. The Treatment Effectiveness Assessment score is the sum of the four responses (minimum = 4, maximum = 40); the Treatment Effectiveness Assessment score will not be computed if the participant did not respond to all four items.

As the sum of four ordinal items, a nonparametric approach to the analysis will be used since it is unlikely the values will meet the necessary normality assumptions for MMRM or ANCOVA

methods. Therefore, the change from screening in Treatment Effectiveness Assessment score at each post-screening timepoint will be compared in each IXT-m200 group versus the placebo group using a Kruskal-Wallis test.

For each comparison and timepoint, the Hodges-Lehmann estimate and 95% confidence intervals for the difference in group medians, and two-sided p-values will be reported.

A waterfall plot, depicting the median change from baseline at each timepoint will be provided for each treatment group. Pseudo-R code for the plot is included in Exhibit 4. Exhibit 5 contains an example of the waterfall plot.

[figure not shown]
Exhibit 4 Pseudo-R Code for TEA Waterfall Plot

```
coltrt <- ifelse(medstrt >= 0,rgb(0.2,0.7,0.9,.75), rgb(1,0.5,0,.75))
colplcbo <- ifelse(medsplcbo >= 0,rgb(0.2,0.7,0.9,.75), rgb(1,0.5,0,.75))

par(mfrow=c(1,2))
barplot(medstrt,ylim=c(min(c(medstrt,medsplcbo)),max(c(medstrt,medsplcbo))),col=coltrt,yla
b="Change from Baseline")
segments(x0=0,x1=4,y0=0,y1=0,lty="dashed")

title('Change from Baseline in TEA Score for IXT-m200 Group')
axis(1, at=1:3, labels=c("Week 13","Week 25", "Week 33"))
barplot(medsplcbo,ylim=c(min(c(medstrt,medsplcbo)),max(c(medstrt,medsplcbo))),col=colplc bo)
title('Change from Baseline in TEA Score for Placebo Group')
axis(1, at=1:3, labels=c("Week 13","Week 25", "Week 33"))
segments(x0=0,x1=4,y0=0,y1=0,lty="dashed")
```

Exhibit 5 TEA Waterfall Plot

Proportion of responders meeting early remission criteria

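### As placed, the exclusion sentence in the TEA paragraph of SAP 4.1.2 contradicts the TEA estimand and the ITT rule; it names no endpoint and its scope must be stated

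*SAP*

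**What the plan says.** **Estimand.** For TEA, SAP Table 2 (section 1.1) asks whether adding the drug would "improve the change from screening in participant-rated quality of life relative to the CBT program alone in treatment-seeking participants regardless of IXT-m200 interruption or discontinuation", whatever the cause. Its handling rule is: "All observations will be used, regardless of whether a participant discontinued treatment early. Missing values will not be imputed".

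**Analysis set.** SAP 4.7.1.2 says "All secondary analyses will use the ITT population". SAP section 3 (Table 5) defines ITT as "all randomized participants categorized by their randomized treatment assignment". The TEA method text in 4.7.1.2 adds no exclusion.

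**Exclusion.** In SAP 4.1.2 the TEA paragraph says that missing scores "will not be imputed. Participants who withdraw or discontinue prior to Week 5, or do not have any reported saliva or self-report use data" in the window from Week 5 to Week 25 are left out of the analysis. No endpoint is named.

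**Protocol.** Section 7.2 separates participants who withdraw from those who are discontinued. The latter are "Participants that will no longer be dosed with study drug but agree to continue participation in other study procedures and assessments". Section 1.3.3 gives them their own schedule, which starts at Week 5 and keeps TEA on Days 85, 169 and 225. Section 9.4.3 analyses the secondary endpoints on ITT with no exclusion of this kind, and SAP 4.13 declares no change from the protocol's analyses.

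**The concern.** A rule that missing scores are not imputed leaves observed scores alone. The sentence that follows it does something else: it removes people, including any TEA scores they have, on grounds unrelated to whether TEA was completed. A programmer cannot apply both that sentence and Table 2.

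Both grounds arise after randomization. Stopping early can follow from treatment, for example after an infusion reaction, and so can disengagement from the app. If the excluded participants differ from the rest, and the excluded share differs between arms, the TEA comparison moves away from the treatment-policy effect that Table 2 defines and towards an effect among those who stayed on treatment or kept reporting. SAP 1.2 records that the study stopped before Cohort 2, so the comparison rests on about 40 versus 20 participants, and each observed score counts.

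**Working it through.** The plan states no figure for TEA, so the main check is a comparison of texts.

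**1. Can observed TEA scores exist for people the sentence removes?**

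| Limb of the sentence | Reading | Is TEA still collected? | Effect |
|---|---|---|---|
| Discontinue before Week 5 | Off drug, still in study (Protocol 7.2) | Yes, at Weeks 13, 25 and 33 (Protocol 1.3.3) | Observed scores discarded |
| Discontinue before Week 5 | Left the study | At most an early-termination assessment | Little discarded |
| Withdraw before Week 5 | Left the study | At most an early-termination assessment | Little discarded |
| No saliva and no self-report data, Weeks 5 to 25 | Either | Yes, if visits are attended: TEA is done at visits (Protocol 8.1.1), the other two come through the app (Protocol 6.1.1) | Observed scores discarded |

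The first row is not hypothetical in design. After an SAE attributed to study drug, dosing ends but the participant is followed to completion (Protocol 6.1.2). A participant found to be pregnant stops dosing but completes the other assessments (Protocol 8.2.6).

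**2. Does any reading reconcile the sentence with Table 2 for TEA?** No. If it is specific to TEA, it conflicts directly. If it is a general rule, it still covers TEA. If it is a stray copy of the sentence used for other endpoints, it is in the wrong place.

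**3. Size, by assumption.** The documents give no rate of stopping before Week 5 and no TEA standard deviation. If a fraction f of an arm is deleted and its mean change is d points worse than that of the rest, the arm mean rises by f × d.

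- 4 of 40 active, d = 8: 4/40 × 8 = 0.8 points; 36 remain.
- 8 of 40 active, d = 8: 8/40 × 8 = 1.6 points; 32 remain.

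The scale runs from 4 to 40. Both lines assume that nobody is deleted from placebo, so the whole shift enters the difference. That is a worst case. With the same d in both arms the shift in the mean difference is (f_active − f_placebo) × d, which is zero when the shares are equal.

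**4. On the planned estimator.** SAP 4.7.1.2 uses Kruskal-Wallis with a Hodges-Lehmann estimate, not means. Simulating the same one-arm inputs (normal changes, SD assumed between 4 and 8, 40 versus 20, 4,000 replicates) gives an average Hodges-Lehmann shift of about 0.63 to 0.75 points in place of 0.8, and 1.35 to 1.54 in place of 1.6.

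**5. Precision.** Only a rough scale is available, because SAP Table 4 concerns the primary endpoint and a t-test. For 40 versus 20 its figures reproduce: 0.780, 0.835 and 0.903 SD against the stated 0.78, 0.84 and 0.90 at 80%, 85% and 90% power. If 10% were excluded from each arm (36 versus 18), the 80% figure becomes 0.82 SD. At 20% (32 versus 16) it becomes 0.88 SD. Equal exclusion therefore costs precision even where it causes no bias.

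**The case against.** The strongest reply is that the sentence may never have been meant for TEA. Near-identical wording appears under the Week 25 responder endpoint (SAP 4.7.1.2) and under the Week 33 responder and complete-abstinence endpoints (SAP 4.8), where a criterion based on drug-use data has some connection to the outcome. The TEA method text does not repeat it. A misplaced copy is a plausible explanation. This stands as an account of how the sentence got there, but it does not make the sentence right where it is.

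Second, a reader might infer that the SAP definitely deletes the scores of everyone who stops drug early. The documents do not settle that. The phrase pairs the two terms that Protocol 7.2 defines, which favours the off-drug meaning. But the SAP adds the word treatment when it means stopping drug (Table 2, section 4.3), and in sections 1.2 and 2.4 the unqualified word reads as leaving the study. On that meaning the first limb costs little. The second limb still bites, though narrowly: it needs neither a saliva result nor a self-report anywhere in Weeks 5 to 25, from someone who passed the app training required for entry.

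Third, a reader might infer a sizeable bias in favour of the drug. The documents do not support that either. The rule applies to both arms, and the dropout figure of up to 50% is not given by arm. The earlier single-dose studies reported no discontinuations for treatment-emergent adverse events (Phase 1) and only grade 1 or 2 events (STAMPOUT). Deletion from the active arm alone is an extreme case, and the direction of any bias is not established.

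**Conclusion.** The contradiction is in the text and holds under every reading of the sentence that covers TEA. How much data it removes depends on what discontinuing means: potentially complete TEA records under the Protocol 7.2 meaning; otherwise mainly the scores of visit attenders with no saliva or self-report data in Weeks 5 to 25. The number affected is unknown and may be small or zero.

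The 0.8 and 1.6 point figures rest on an assumed 10% or 20% deletion from the active arm only and an assumed 8-point deficit. They illustrate a mean shift and do not forecast the planned estimate.

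A reader might also infer that the primary endpoint loses participants under the same sentence. SAP 4.6.1 specifies ITT and counts missed screens and weeks after withdrawal as not abstinent, so that inference is not supported, though a one-line confirmation would close it.

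For one of several secondary endpoints in an exploratory study without multiplicity adjustment, this should be corrected, but it does not threaten the main result.

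**What to change.** Delete the sentence from the TEA paragraph of SAP 4.1.2 and replace it with:

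> At each timepoint (Weeks 13, 25 and 33), all ITT participants with a screening TEA and a TEA at that timepoint are analysed as randomized, whatever their dosing, saliva or self-report status.

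Inclusion is set per timepoint because SAP 4.7.1.2 tests each visit separately and nothing is imputed.

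If the sentence was meant for other endpoints, name them, say whether discontinuing means stopping drug or leaving the study, and reconcile it with their own rules. For Week 25 early remission, Table 2 and the first paragraph of 4.1.2 count missing values as non-response, while 4.7.1.2 excludes the participants. The same exclusion is written for the Week 33 responder and complete-abstinence endpoints in 4.8. Confirm in one line that no such exclusion applies to the primary endpoint.

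The cost is SAP wording. The scores are already collected, and no visits or analyses are added.
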